3. STATISTICAL ANALYSIS

3.1 Participant Information

3.1.1 Disposition of Study Participants

The number of participants screened for this study, the number of screen failures and the number of participants who received at least one dose of IP will be summarized using the Enrolled Population. Reasons for screen failure will be provided in the data listing.

Study completion and withdrawal from the double-blind phase will be summarized by treatment group for all enrolled participants. The summary table will include the numbers of participants included in each analysis set and those who completed or did not complete the study, along with the reasons for discontinuation (adverse events, protocol deviation, lost to follow-up, death, etc.) of study treatment and discontinuation from study will be summarized.

Reason for discontinuation from study will be provided in the data listing.

In addition, a summary of the number of participants included in each analysis set will be presented.

3.1.2 Protocol Deviations

Protocol deviations will be identified to measure adherence to key aspects of the protocol before the database freeze/lock for the relevant analysis. Specific data fields that will be examined to identify protocol deviation or violations include inclusion/exclusion criteria and deviations identified by the investigator. The protocol deviations will be summarized by deviation category based on the Safety Population. A data listing will also be provided.

3.1.3 Demographics and Baseline Characteristics

Descriptive summary statistics (n, mean, standard deviation, median, 25th and 75th percentiles, minimum, and maximum) and/or frequency distributions (count and percentage), as appropriate, will be provided by treatment group for the Safety Population.

Demographic characteristics summarized will include:

- Age
- Age group (12 to < 18 yrs, ≥18 yrs)
- Sex (male, female)
- Race/ethnicity
- Height (cm)
- Weight (kg)
- Weight group (<40 kg, ≥40 kg)
- Body Mass Index (BMI; kg/m²)

Baseline characteristics summarized will include:

- Etiology of SE (Cerebrovascular accidents, Anoxia or hypoxia, etc.)
- Pre-infusion duration of SE
- Number of failed AEDs
- Previous epilepsy history
- Status Epilepticus Severity Score (STESS)
- Richmond Agitation and Sedation Scale (RASS)
- Full Outline of UnResponsiveness (FOUR) Score
- Clinical Global Impression of Severity (CGI-S)

3.1.4 Medical History

Medical history will be coded with the Medical Dictionary for Regulatory Activities (MedDRA) Terminology version 22.0 or higher. The number and percentage of participants with medical history will be summarized by System Organ Class (SOC) and Preferred Term (PT) based on the Safety Population.

3.1.5 Prior and Concomitant Medications

Prior medications are defined as medications that started prior to the initiation of IP. Concomitant medications are defined as medications that started after the initiation of IP or started before the administration of the study drug and ongoing after the IP initiation.

All investigator terms for prior and concomitant medications recorded on the Case Report Form (CRF) will be coded using the World Health Organization (WHO) Anatomical Therapeutic Chemical (ATC) drug dictionary (WHO Drug Dictionary, March 1, 2021).

The number and percentage of participants with prior and concomitant medications will be summarized by ATC level 2 and PT based on the Safety Population, by treatment group and overall. Listings will also be provided for all prior and concomitant medications. Listing will identify treatments as either prior (before the initiation of IP) or concomitant (from initiation of IP to end of follow-up visit/contact).

In addition, benzodiazepines, AEDs, and anesthesia medications, as collected in a separated CRF, will be summarized in a similar fashion. A separate listing and summary table will be presented for Benzodiazepines, AEDs, and IV anesthesia.

3.1.6 Investigational Product Infusion Summary

Investigational product will be administered as a 48-hour continuous infusion, which includes an initial 3-minute bolus and ends with a 12-hour taper based on [Table 4](#) and [Table 5](#). The total administered dose (mg) for IP infusion and duration of IP infusion will be summarized based on the Safety Population.

Table 4. Dosing for Participants ≥ 40 kg (on a mg/hour basis)

Days	Start Time from IP Initiation	IP Dose	IP Infusion Rate (mL/hour)	Duration
Day 1	0 hours: bolus dose via syringe or infusion pump	30 mg ^a	N/A	3 minutes (0.05 hours)
Day 1	0 hours through 2 hours following IP initiation: continuous infusion, started with bolus	80 mg/hr	80	2 hours
Day 1	2 hours through 12 hours following IP initiation	40 mg/hr	40	10 hours
Day 1	12 hours through 24 hours following IP initiation	20 mg/hr	20	12 hours
Day 2 ^b	24 hours through 36 hours following IP initiation	20 - 45 mg/hr	20 - 45	12 hours
	Taper			
Day 2 ^c	36 through 48 hours following IP initiation (12-hour taper)	13 - 30 mg/hr	13 - 30	4 hours
		9 - 20 mg/hr	9 - 20	4 hours
		6 - 13 mg/hr	6 - 13	4 hours

IP = investigational product.

- a. The 30 mg bolus is administered over ~3 minutes.
- b. On Day 2 (24 through 36 hours), the continuous infusion rate can be increased from 20 mg/hour to a maximum rate of 45 mg/hour at any time, if needed, to manage seizure relapse or other medical reason.
- c. To taper the IP, the infusion rate at the 36-hour following IP initiation timepoint will be reduced by 33.3% every 4 hours until the infusion rate is stopped or if the infusion rate becomes too low to sustain the infusion line, at which point it will be stopped. The first taper will be 33.3% from the current infusion rate (e.g., if the current infusion rate is 20 mg/hr, the first taper will be 13 mg/hr) the second taper will be 33.3% from the first tapered infusion rate (e.g., if the current infusion rate is 20 mg/hr, the second taper will be 9 mg/hr), and the final taper will be 33.3% from the previous tapered infusion rate (e.g., if the current infusion rate is 20 mg/hr, the final taper will be 6 mg/hr). If, in the investigator's judgment, the taper needs to start at an earlier timepoint during the treatment period, the infusion rate at the start of the first taper will be decreased by 33.3% every 4 hours as described.

Table 5. Dosing for Participants < 40 kg (on a mg/kg/hour basis)

Days	Start Time from IP Initiation	IP Dose	IP Infusion Rate (mL/kg/hour) ^a	Duration
Day 1	0 hours: bolus dose via syringe or infusion pump	0.75 mg/kg ^b	N/A	3 minutes
Day 1	0 hours through 2 hours following IP initiation continuous infusion, started with bolus	2.0 mg/kg/hr		2 hours
Day 1	2 hours through 12 hours following IP initiation	1.0 mg/kg/hr		10 hours
Day 1	12 hours through 24 hours following IP initiation	0.50 mg/kg/hr		12 hours
Day 2 ^c	24 hours through 36 hours following IP initiation	0.50 – 1.125 mg/kg/hr		12 hours
	Taper			
Day 2 ^d	36 through 48 hours following IP initiation (12-hour taper)	0.34 – 0.75 mg/kg/hr		4 hours
		0.22 – 0.51 mg/kg/hr		4 hours
		0.15 – 0.34 mg/kg/hr		4 hours

IP = investigational product.

- Reference the Pharmacy Manual for IP infusion rates based on mg/kg/hour dosing.
- The 0.75 mg/kg bolus is administered over ~ 3 minutes.
- On Day 2 (24 through 36 hours), the continuous infusion dose can be increased from 0.5 mg/kg/hour to a maximum dose of 1.125 mg/kg/hour at any time, if needed, to manage seizure relapse or other medical reason.
- To taper the IP, the infusion rate at the 36-hour following IP initiation timepoint will be reduced by 33.3% every 4 hours until the infusion rate becomes too low to sustain the infusion line, at which point it will be stopped. The first taper will be 33.3% from the current infusion rate (e.g., if the current infusion rate is 0.50 mg/kg/hr, the first taper will be 0.34 mg/kg/hr), the second taper will be 33.3% from the first tapered infusion rate (e.g., if the current infusion rate is 0.50 mg/kg/hr, the second taper will be 0.22 mg/kg/hr), and the final taper will be 33.3% from the previous tapered infusion rate (e.g., if the current infusion rate is 0.5 mg/kg/hr, the final taper will be 0.15 mg/kg/hr). If, in the investigator's judgment, the taper needs to start at an earlier timepoint during the treatment period, the infusion rate at the start of the first taper will be decreased by 33.3% every 4 hours as described.

3.2 Efficacy Analysis

Statistical hypotheses testing will be performed for the co-primary and key secondary endpoints for the double-blind phase. To control the family wise type I error, the testing will be performed sequentially (the coprimary endpoints will be tested simultaneously), in the order as listed. Subsequent testing will only be performed if the prior tests are significant.

The interim analysis will be performed using the logistic regression method described below. Due to the limited amount of data, the data after the interim analysis will be analyzed using the Boschloo test. If the p-value (one-sided) of the interim analysis is p_1 and the p-value (one-sided) from after the interim analysis is p_2 , and let Φ^{-1} be the inverse Normal function, a final Z score is calculated as

$$Z = \sqrt{\frac{2}{3}}\Phi^{-1}(1 - p_1) + \sqrt{\frac{1}{3}}\Phi^{-1}(1 - p_2)$$

The Z-test using the above Z score will be used as the final test.

The efficacy analysis of the response rates observed for each co-primary endpoint will be conducted by using logistic regression methods. The model will include terms for treatment group and baseline STESS as a covariate. The analysis will be based on the ITT population. Model-based point estimates (i.e., odds ratio), 95% confidence intervals and p-values will be reported. In addition, the point estimate of difference of the proportions of participants achieving either and both co-primary endpoints between two treatment arms will be provided. The 95% confidence interval will be provided using Clopper-Pearson method.

The concerned estimand is defined by its attributes below:

- Population: the target study population comprises participants with status epilepticus who also meet the inclusion and exclusion criteria as specified in the study protocol. The analysis population is the Intent-to-Treat (ITT) population as defined in [Section 2](#).
- Variable for the first co-primary: a binary response variable indicating a successful response which is defined as SE termination beginning within 30 minutes of IP initiation without use of medications for the acute treatment of SE.
- Variable for the second co-primary: a binary response variable indicating absence of IV anesthesia for 36 hours following IP initiation.
- Intercurrent events:
 - Discontinuation of study treatment due to any reason
 - Death
- Population-level summary: odds ratio between treatment groups.

The participants with any of the listed intercurrent events will be considered as a treatment non-responder. To deal with other intercurrent events, a treatment policy approach will be adopted. Due to the nature of the disease and short observational period, occurrence of intercurrent events is expected to be low.

3.2.1.2 Sensitivity Analysis

The primary efficacy analysis will be repeated in the PP population.

In addition to logistic regression, response rates for both primary endpoints will also be analyzed using the Boschloo test.

If missing data on the first or second co-primary endpoint exceeds 5%, a tipping point analysis will be performed for that endpoint. Assuming N_c participants have missing primary outcome data in the control group and N_t participants have missing primary outcome data in the treatment group, the primary analysis will be performed to assume 0 to N_c control participants achieved the primary outcome and 0 to N_t treatment group participants achieved the primary outcome. All $(N_c+1)(N_t+1)$ outcomes will be enumerated in a grid that shows the treatment effect and p-value and the ‘tipping point’ when the result would cease to be statistically significant. Model averaging will be used to account for multiple possible scenarios contributing to the same number of missing data values.

3.2.1.3 Subgroup Analysis

The primary efficacy analysis will be repeated for subgroups defined by the following baseline variables:

- Age group (12-18 yrs, ≥ 18 yrs)
- Sex (male, female)
- Weight group (<40 , ≥ 40 kg)

Subgroups could be collapsed if the number of participants in some subgroups is too small.

3.2.2 Key Secondary Efficacy Endpoints

3.2.2.1 Primary Analysis

The key secondary efficacy endpoints are:

1. Time to SE cessation following IP initiation
2. Proportion of participants with no progression to IV anesthesia for 72 hours following IP initiation

Time to SE cessation will be assessed for the first 72 hours following IP initiation. Observations for cessation of SE that occurs at a time greater than 72 hours will be censored at 72 hours. Key secondary endpoints will be compared between GNX and placebo groups in the ITT population. The hypotheses for the key secondary endpoints will be tested only if both co-primary endpoints are statistically significant. The key secondary endpoints will be tested in the order listed, at the same alpha level of significance as the primary endpoints. More details can be found in [Section 3.5](#).

For time to SE cessation following IP initiation, the comparison of the survival curves of time to SE cessation between treatment groups will be conducted by a log-rank test. The quartiles (1st [25% percentile], 2nd [median], 3rd [75% percentile]) and the associated 95% CI will be provided based on the Kaplan-Meier estimate of the survival curves. participants without SE cessation before 72 hours post dose initiation or at the time of discontinuation will be censored at 72 hours or the time of discontinuation, whichever is earlier; death before SE cessation will be censored at 72 hours.

The proportion of participants with no progression to IV anesthesia for 72 hours following IP initiation will be summarized based on the ITT population. Descriptive statistics, count and percentage of participants will be summarized. This key secondary efficacy endpoint will be analyzed using logistic regression, the same analysis method as for the co-primary endpoints.

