5.2.2 Prohibited Treatment

If a participant progresses at any time during the study to an IV anesthetic (e.g., midazolam, propofol, thiopental, or pentobarbital) given with the primary intent specifically to treat seizures or achieve burst suppression IP administration will be discontinued without taper but the participant will continue in the study. Additional details can be found in [Section 4.5](#).

Concomitant use of IV products containing Captisol® during IP administration is prohibited (see exclusion criterion #7 and Appendix 4).

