7.2.2.7 Status Epilepticus Cessation Questionnaire

For this study, SE Cessation is defined as the beginning of the first 30-minute epoch following IP initiation in which SE burden is no longer fulfilled (<20% ictal burden and is at least 50% less during the 30 minutes prior to IP initiation). This questionnaire should be collected as close as possible to 24 and 72 hours following IP initiation. Reference [Table 1](#).

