13 APPENDICES

APPENDIX 1 STATUS EPILEPTICUS CESSATION GUIDE

Status epilepticus cessation will be based on investigator judgment, guided by the following clinical and electrographic features:

1. The first 30-minute SE free period after IP initiation denotes the onset of SE cessation
2. Electrographically SE cessation should coincide with the beginning of the first 30-minute epoch of EEG which demonstrates seizure burden <20% and at least 50% less than during the 30 minutes prior to IP initiation
3. For the first co-primary endpoint only, SE cessation observed without administration of medications for the acute treatment of SE* from the time of IP initiation through 30 minutes following the onset of SE cessation

*Medications for the acute treatment of SE are defined as AEDs administered to abort ongoing SE or prevent imminent recurrence of SE based on clinical or EEG evidence. This definition excludes maintenance doses of AEDs or medications with anticonvulsant properties used for other reasons, such as procedural sedation.

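### The first key secondary leaves 'discontinuation' undefined and lets SE cessation under IV anesthesia count as an event, which pulls the comparison toward the null

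*SAP*

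**What the plan says.** For the first key secondary, SAP 3.2.2.1 states that "the comparison of the survival curves of time to SE cessation between treatment groups will be conducted by a log-rank test", in the ITT population over 72 hours. Participants without cessation "will be censored at 72 hours or the time of discontinuation, whichever is earlier; death before SE cessation will be censored at 72 hours". The kind of discontinuation is not named. SAP 3.2.3.2 and 3.2.3.3, on other time-to-event endpoints, do specify discontinuation from the study.

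The event is defined in Protocol 7.2.2.7: "SE Cessation is defined as the beginning of the first 30-minute epoch following IP initiation in which SE burden is no longer fulfilled". The definition is by ictal burden and sets no condition on how the burden fell. Appendix 1 of the protocol adds a medication condition, but restricts it: "For the first co-primary endpoint only, SE cessation observed without administration of medications for the acute treatment of SE".

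When an IV anesthetic is given to treat seizures, Protocol 5.2.2 says that "IP administration will be discontinued without taper but the participant will continue in the study".

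The intercurrent-event rules do not reach this endpoint. In the co-primary estimand of SAP 3.2.1.1, where IP discontinuation and death are listed, "The participants with any of the listed intercurrent events will be considered as a treatment non-responder". The treatment-policy statement in Protocol 10.4.1 also names only the co-primary analyses. The sole sensitivity analysis for the key secondaries (SAP 3.2.2.2) is a per-protocol repeat under the same event rule.

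**The concern.** Each reading of the censoring term creates a problem.

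- **Study discontinuation.** An anesthetized participant stays in the study. If the anesthetic brings ictal burden below threshold within 72 hours, the participant is scored as having achieved SE cessation. Protocol 10.4.1 frames the primary efficacy objective as cessation without escalation to IV anesthesia, so here the escalation can supply the event.
- **IP discontinuation.** Starting anesthesia for SE stops IP, so a participant without cessation is censored at the moment treatment fails, because it failed. That is informative censoring.

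Anesthesia is not a marginal event. Inclusion criterion 3b requires that IV anesthesia be the likely next treatment, and the sample-size assumptions imply that it is common. The endpoint is first in the key-secondary sequence, so missing it also blocks the test of no IV anesthesia for 72 hours. An unresolved reading of a tested endpoint also leaves a choice that could be made after the data are seen.

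**Working it through.** **Expected anesthesia.** Protocol 10.2 assumes response of at least 75% on ganaxolone and at most 45% on placebo for each co-primary. For the 36-hour co-primary the complements are 1 − 0.75 = 25% and 1 − 0.45 = 55% progressing to IV anesthesia.

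**The plan's nearest stated figure.** No power is given for time to SE cessation. For each co-primary the plan claims at least 90% with 62 per arm at two-sided 5%. With a pooled rate of 0.60:

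power = Φ{[0.30 − 1.96·√(2·0.60·0.40/62)] / √[(0.75·0.25 + 0.45·0.55)/62]} = Φ{(0.30 − 0.1725)/0.0838} = Φ(1.52) = 0.936.

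This agrees with the plan.

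**Rules compared.**
- A: any cessation within 72 h is an event, including under anesthesia (study reading).
- B: anesthesia before cessation censors at its start (IP reading).
- C: anesthesia before cessation is a non-event held to 72 h, as the SAP already does for death.

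**Assumptions, none of them in the documents.**
- The 75% and 45% who respond within 30 minutes do so at uniformly distributed times.
- Anesthesia starts at 0.5 h plus an exponential time with median 1, 4 or 12 h, and by 36 h at the latest.
- A fraction q = 60% or 90% of those anesthetized meet the cessation definition within 1 h.
- Either every 30-minute non-responder is anesthetized (full overlap), or anesthesia is independent of 30-minute response (independence). In the independent case, half of the non-responders without anesthesia stop later, by 24 h.

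**Cessation by 72 h, rules A and C.**
- Full overlap, placebo: C 0.45; A 0.45 + 0.55q = 0.78 or 0.945. Ganaxolone: C 0.75; A 0.75 + 0.25q = 0.90 or 0.975. The 30-point difference shrinks to 12 or 3.
- Independence, placebo: C 0.45 + 0.55·0.45·0.5 = 0.574; A adds 0.55·0.55·q, giving 0.755 or 0.846. Ganaxolone: C 0.75 + 0.25·0.75·0.5 = 0.844; A adds 0.25·0.25·q, giving 0.881 or 0.900. The 27-point difference shrinks to 12.6 or 5.4.

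The simulated placebo Kaplan-Meier values agree: 44–59% under C and 75–95% under A. Under B they are 44–73%.

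**Log-rank power**, 50 per arm (100 randomized), two-sided 0.0343, 2,000 trials per scenario (Monte Carlo standard error about 1 point). Ranges are over the three anesthesia timings:

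| Scenario | A | B | C |
|---|---|---|---|
| Full overlap, q = 60% | 67–70% | 80–83% | 80–83% |
| Full overlap, q = 90% | 60–62% | 81–82% | 81–82% |
| Independence, q = 60% | 63–66% | 76–83% | 85–86% |
| Independence, q = 90% | 44–52% | 74–81% | 84% |

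Taken scenario by scenario, A loses 11 to 41 points against C, and B loses 0 to 10. With 62 per arm at 0.05, the ranges are A 55–82%, B 85–93% and C 92–95%.

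B equals C under full overlap because every cessation without anesthesia then comes before the first anesthetic. The curves are unchanged there too.

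These are single-stage log-rank tests. The SAP's fixed-weight combination of data before and after the interim was not simulated, so the contrast between rules matters more than the absolute power.

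**The case against.** **The study reading is the natural one.** IP ends by about 48 hours for everyone, so if stopping IP censored, the 72-hour limit would never apply to a participant without cessation. This stands, and the censoring branch is the lesser problem. The words are still missing, and SAP 3.1.1 and 3.2.1.1 also use discontinuation for study treatment.

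**Counting cessation however achieved may be deliberate.** Appendix 1 restricts the medication condition explicitly, which suggests that the sponsor considered it. A treatment-policy estimand is coherent here, and a separate rule for death is compatible with it. A reader might infer that the rule cannot be treatment policy, but the documents do not support that. They do not state that choice for this endpoint either.

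**Nothing is contradicted.** A reader might infer that SAP 3.2.1.1 and 3.2.2.1 conflict. The non-responder rule belongs to the co-primary estimand, and another endpoint may handle the same events differently.

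**The rule does not favor ganaxolone.** It applies to both arms, and in every scenario the distortion runs toward the null. The cost is power and interpretability, on an endpoint tested only after both co-primaries succeed.

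**The size is assumption-driven.** A reader might infer that both arms would read near 100%. That needs every anesthetic to work and every other non-responder to stop. Protocol 7.2.2.8 itself defines SE that continues or recurs despite anesthesia.

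**The interim has been run** on 83 participants (Protocol 10.7, SAP 3.5). Changing the main event definition now is debatable; clarifying the censoring term and adding an analysis is much less so.

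**Conclusion.** The point holds as a gap in the event and censoring rules of a formally tested endpoint. As written, SE cessation under IV anesthesia can count as an event, and the censoring term has two readings with different consequences.

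On the more natural study reading, at 50 per arm and alpha 0.0343, log-rank power is about 44–70%, against 80–86% if anesthesia before cessation is held as a non-event. Apparent placebo cessation by 72 hours is 75–95% instead of 44–59%. On the IP reading the censoring is informative, but the power loss is 0–10 points.

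These figures rest on the plan's 75% and 45% rates and on assumed timings and anesthetic success. They are ranges, not predictions for this trial. What follows from the design is the direction: more anesthesia on placebo brings the arms closer together.

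**What to change.** In SAP 3.2.2.1, specify discontinuation from the study and say that stopping IP does not censor. State explicitly whether cessation after the start of IV anesthesia for SE is an event.

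In SAP 3.2.2.2, prespecify an analysis that holds participants who start IV anesthesia for SE before cessation as non-events to 72 hours, as the SAP already does for deaths. Add a version that treats other acute SE medication the same way, since cessation after those drugs raises the same attribution question.

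If the sponsor prefers this rule as the main analysis, the change should be made and documented while the sponsor is still blinded. The SAP should record that it comes after the interim and keep the count-all version as supportive.

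The cost is one or two extra analyses and a documented post-interim SAP change. No new data should be needed: Protocol 5.2 records each benzodiazepine, AED and anesthetic dose separately during IP and for 120 hours of follow-up, and the schedule of assessments records the reason for each AED.
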